18.5.2 Incomplete Stop Date and Time

The following rules will be applied to impute the missing numerical fields. If the imputed stop date is before the start date (imputed or non-imputed start date), then the imputed stop date will be equal to the start date.

Missing day and month

- If the year of the incomplete stop date is the same as the year as of the date of the last dose of investigational product, then the day and month of the date of the last dose of investigational product will be assigned to the missing fields
- If the year of the incomplete stop date is before the year of the date of the last dose of investigational product, then 31 December will be assigned to the missing fields
- If the year of the incomplete stop date is after the year of the date of the last dose of investigational product, then 01 January will be assigned to the missing fields.

Missing month only

- The day will be treated as missing and both month and day will be replaced according to the above procedure.

Missing day only

- If the month and year of the incomplete stop date are the same as the month and year of the date of the last dose of investigational product, then the day of the date of the last dose of investigational product will be assigned to the missing day
- If either the year is before the year of the date of the last dose of investigational product or if both years are the same but the month is before the month of the date of the last dose of investigational product, then the last day of the month will be assigned to the missing day
- If either the year is after the year of the last dose of investigational product or if both years are the same but the month is after the month of the date of the last dose of investigational product, then the first day of the month will be assigned to the missing day.

Missing Time

- If the time is missing it will be imputed as 23:59.

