9. PRIOR AND CONCOMITANT MEDICATION

Version WHODRUG 2017MAR01 DDE (B2 format) will be used to classify prior and concomitant medications by preferred term. Medications will also be coded by the Anatomical Therapeutic Chemical (ATC) classification system.

Medications starting within 30 days before the first dose of investigational product and up to the end of the follow-up period will be collected on the CRF.

Prior medication is defined as any medication with the start date prior to the date of the first dose of investigational product. Concomitant medication is defined as any medication with a start date prior to the date of the first dose of investigational product and continuing after the first dose of investigational product or with a start date after the date of the first dose of investigational product.

Concomitant medication usage will be summarized by the number and proportion of subjects receiving each medication by preferred term, by ethnic group and rhPTH(1-84) dose for the Safety Analysis Set. Medications can be counted both as prior and concomitant medication. Multiple medication usage by a subject in the same category will be counted only once.

Concomitant medications will be assigned to the dose(s) with which they are concomitant. A medication is concomitant with a dose of rhPTH(1-84) if the subject received that medication any time between the time when that dose of rhPTH(1-84) was received and when the next dose of rhPTH(1-84) was received, or in the case of the last dose, until the end of the follow-up period. Therefore, a medication may be concomitant with more than one dose.

All prior and concomitant medication will be listed.

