18.5 Missing Date Information for Prior or Concomitant Medications

For prior or concomitant medications, incomplete (i.e., partially missing) start date and/or stop date will be imputed. When the start date and the stop date are both incomplete for a subject, impute the start date first.

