18.5.1 Incomplete Start Date and Time

The following rules will be applied to impute the missing numerical fields. If the stop date is complete and the imputed start date is after the stop date, then the start date will be imputed using the stop date.

Missing day and month

- If the year of the incomplete start date is the same as the year of the date of the first dose of investigational product, then the day and month of the date of the first dose of investigational product will be assigned to the missing fields
- If the year of the incomplete start date is before the year of the date of the first dose of investigational product, then December 31 will be assigned to the missing fields
- If the year of the incomplete start date is after the year of the date of the first dose of investigational product, then 01 January will be assigned to the missing fields.

Missing month only

- The day will be treated as missing and both month and day will be replaced according to the above procedure.

Missing day only

- If the month and year of the incomplete start date are the same as the month and year of the date of the first dose of investigational product, then the day of the date of the first dose of investigational product will be assigned to the missing day
- If either the year is before the year of the date of the first dose of investigational product or if both years are the same but the month is before the month of the date of the first dose of investigational product, then the last day of the month will be assigned to the missing day
- If either the year is after the year of the date of the first dose of investigational product or if both years are the same but the month is after the month of the date of the first dose of investigational product, then the first day of the month will be assigned to the missing day.

Missing/Incomplete Time

- If the time is missing and the date is complete and is the same as the date of the first dose of investigational product, or the date is imputed to be this date, then the time will be set to the time of the first dose of investigational product. Otherwise, missing times will be imputed as 00:00.
- If the minutes are given but the hour is not, then the time will be regarded as completely missing and handled as above. If the hour is given but the minutes are not, then if the hour is the same as the hour of the first dose of investigational product, then the minutes of that

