18.6 Missing Date and Time Information for Adverse Events

For AEs, only incomplete (i.e., partially missing) start dates will be imputed. Incomplete stop dates will not be imputed.

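### SAP 18.5.1 checks an imputed start only against a complete stop date, so a record with a year-only start and a stop in an earlier month is moved onto the first 100 µg dose

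*SAP*

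**What the plan says.** For medications with two partial dates, SAP 18.5 fixes the order: "When the start date and the stop date are both incomplete for a subject, impute the start date first".

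SAP 18.5.1 handles a start whose month is missing. If the recorded year is the year of the first dose, "then the day and month of the date of the first dose of investigational product will be assigned to the missing fields". When a date is imputed to that day and the time is missing, "then the time will be set to the time of the first dose of investigational product". The only check against the stop takes the start from the recorded stop in one situation: "If the stop date is complete and the imputed start date is after the stop date, then the start date will be imputed using".

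SAP 18.5.2 sets a stop with only the day missing, in a month before the last-dose month, to the last day of the recorded month. A missing stop time becomes 23:59. It then adds a rule that raises an earlier stop to match the start: "If the imputed stop date is before the start date (imputed or non-imputed start date), then the imputed stop date will be equal".

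For adverse events, SAP 18.6.1 adopts the start rules of 18.5.1, and 18.6 says of the other end: "Incomplete stop dates will not be imputed".

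Two classification rules use these dates. SAP 9 assigns a medication to a dose "if the subject received that medication any time between the time when that dose of rhPTH(1-84) was received" and the next dose (for the last dose, the end of follow-up). SAP 11.1 counts an event as treatment-emergent if its start date/time is at or after the first dose, and allocates it to the last dose taken at onset.

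**The concern.** A stop recorded as 'Apr 2017' shows that the drug or event ended before a dose in May, just as '20 Apr 2017' does. The SAP uses the second to hold the start back and ignores the first. For a medication, an imputed start then displaces a stop month that the site recorded. For an adverse event, the derived onset falls after the recorded stop month.

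Every subject's first dose is 100 µg (SAP 2.1), so every such error lands in the 100 µg column. Protocol 9.9.2 bases the direct safety comparison of the two ethnic groups on that column, and each group has 12 subjects. Pre-dose medication use would be shown as concomitant with 100 µg, and a pre-dose event as a 100 µg TEAE.

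**Working it through.** The plan gives no figure to reproduce. The check applies the rules literally to example records.

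**Assumed dates.** First dose 15 May 2017, within the planned May to June 2017 period in the protocol synopsis. Last dose 15 May (Caucasian) or 21 May (Japanese, Day 7).

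**Medication, start '2017', stop 'Apr 2017'.**
1. The start is imputed first (18.5). The year matches the dosing year, so start = 15 May 2017 at dose time (18.5.1).
2. The check in 18.5.1 does not apply, because the stop is not complete.
3. Stop = 30 Apr 2017, the last day of the recorded month (18.5.2).
4. 30 Apr is before 15 May, so the stop is raised to 15 May 2017, 23:59 (18.5.2).
5. Under SAP 9 the drug is concomitant with 100 µg. It is no longer a prior medication, because that needs a start before the first-dose date.

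The result is the same in both groups.

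**Adverse event, same dates.** Step 1 applies through 18.6.1; steps 3 and 4 do not, because event stop dates are not imputed. Onset is 15 May at dose time and the stop remains 'Apr 2017'. The event meets the TEAE rule and is allocated to 100 µg.

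**Day 1 adverse event, start time missing, stop time before the dose.** With an assumed dose at 09:00 and stop at 08:00, the missing start time becomes 09:00. The check compares dates, and 15 May is not after 15 May, so it does not apply. The event starts after it ended and is a TEAE.

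**Which patterns fail.** Take every start/stop pair in the 60 days before 15 May, with start no later than stop: 60 × 61 / 2 = 1830 pairs. In 46 × 47 / 2 = 1081 of them the stop falls in April or earlier, so that the month alone shows a pre-dose end. The table counts pairs whose start is imputed to the first dose.

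| Start recorded as | Complete stop | Stop with day missing |
|---|---|---|
| Full date | 0 of 1830 | 0 of 1081 |
| Day missing | 0 of 1830 | 0 of 1081 |
| Year only | 0 of 1830 | 1081 of 1081 |

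This shows which pattern fails. It is not an estimate of how often the pattern occurs.

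**Size.** One affected subject adds 1/12 = 8.3 percentage points to a 100 µg cell, if not already counted there. The documents do not give the number of records. Assuming 0 to 2, the range for one cell in one group is 0 to 2/12 = 16.7 points.

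**With the start capped at the latest date compatible with the stop.** For '2017' / 'Apr 2017' the start becomes 30 Apr and the stop stays 30 Apr. The drug is prior only, and the event is not a TEAE. Seven other partial-date combinations tried in each group do not change.

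**The case against.** The strongest reply is that the pattern hardly arises. SAP 9 describes collecting medications that start within 30 days before the first dose. A drug meeting that limit and stopped in April, with dosing on 15 May, must have started in April, so its start month is known. Adverse events are collected only from consent, and screening lasts at most 28 days (Protocol 7.1.1, 8.1). An event with a known stop month and no start month would have to arise inside that window. Subjects are confined from Day -1, so a Day 1 event with a stop time and no start time is also unlikely.

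Most of this stands for adverse events. It is weaker for medications, because Protocol 5.1 covers treatment received within 30 days of dosing, whenever it began. A long-used drug with a vague start and a stop in the previous month fits that definition.

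A second reply is that placing uncertain records on treatment is conservative, in line with SAP 18.7 and 18.8, where missing severity becomes severe and missing causality becomes related. That is reasonable for unknown fields. Here the end before dosing is recorded, and the SAP itself gives up the conservative choice when the stop date is complete.

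A reader might infer more than the documents support:
- *That 18.5.2 also moves adverse event dates.* It does not; 18.6 and 18.6.2 exclude stop imputation for events.
- *That any record ending before dosing is at risk.* Among the date patterns, a complete stop date or a known start month gives the right answer.
- *That a subject could appear to breach the 14-day medication restriction.* No rule derives eligibility or deviations from imputed dates. Eligibility is confirmed before dosing (Protocol 4.1, 7.1.1).
- *That the stop-raising sentence should be deleted.* It does useful work. With first and last dose on 28 May, start 'Jun 2017' and stop '2017', the rules give start 1 June and stop 28 May. The sentence repairs the stop to 1 June; without it, the stop precedes the start.

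**Conclusion.** The point holds in a narrow form and is minor. Read literally, SAP 18.5, 18.5.1 and 18.5.2 date a medication with a year-only start in the dosing year and a stop in a month before the first-dose month to the first dose, replacing the recorded stop month. Through 18.6.1, an adverse event with those dates becomes a 100 µg TEAE, as does a Day 1 event with no start time and a pre-dose stop time.

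Few or no records are expected, and the assumed 0 to 2 has no source in the documents. The figure of 8.3 points per subject rests on 12 per group and on the subject not already being in the cell. PK results, and so the primary objective, are unaffected, and no effect on eligibility is shown. The change is worth making because a written rule gives a result that contradicts recorded data and is cheap to correct.

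**What to change.** 1. In SAP 18.5.1, extend the check to read: *If the recorded stop information (complete or partial date, or time on the same date) shows that the medication or AE ended before the first dose, the imputed start is set no later than the latest date/time compatible with that stop. No recorded start field is overridden.*
2. State in 18.6.1 that this applies to adverse events.
3. Keep the sentence in 18.5.2 that raises the stop to the start, and add: *An imputed start does not change a recorded stop month or year.* The June example above is still repaired, because its recorded year stays 2017.

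The order of imputation in 18.5 can stay, since the new check uses the stop as recorded. The cost is a few lines of SAP text and of date-derivation code before database lock, with no change to data collection or design.

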18.6 Missing Date and Time Information for Adverse Events

For AEs, only incomplete (i.e., partially missing) start dates will be imputed. Incomplete stop dates will not be imputed.

18.6.1 Incomplete Start Date and Time

Follow same rules as in Section 18.5.1.

18.6.2 Incomplete Stop Date and Time

Not applicable.

18.7 Missing Severity Assessment for Adverse Events

If severity is missing for an AE starting prior to the date of the first dose of investigational product, then a severity of “Mild” will be assigned. If the severity is missing for an AE starting on or after the date of the first dose of investigational product, then a severity of “Severe” will be assigned. The imputed values for severity assessment will be used for incidence summaries, while the actual values will be used in data listings.

18.8 Missing Relationship to Investigation Product for Adverse Events

If the relationship to investigational product is missing for an AE starting on or after the date of the first dose of investigational product, a causality of “Related” will be assigned. The imputed values for relationship to the investigational product will be used for incidence summaries, while the actual values will be presented in data listings.

18.9 Character Values of Clinical Laboratory Variables

If the reported value of a clinical laboratory variable cannot be used in a statistical analysis due to, for example, that a character string is reported for a numerical variable (e.g. <5), then the appropriately determined coded value will be used in the statistical analysis. However, the actual values as reported in the database will be presented in data listings.

